## 5) Study Timelines

- Study will begin after IRB approval
- Patient recruitment will take place over two years, however this may be longer depending on the number of patients who require definitive surgery
- The duration of the subject's participation in the study will conclude at two year postoperatively
- The primary analysis will be complete within 3 years of the study start time

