## PROTOCOL TITLE: Staged External Fixation of Acute Calcaneal Fractures

Clinicians favoring an open technique have sought ways to minimize soft tissue complications by using a temporary external fixator as similar to the often utilized staged management of tibial plateau and tibial plafond fractures. This delay is necessary for soft tissue swelling to subside prior to surgery with the external fixator allowing for prevention of early clot and fibrinous material between malaligned fracture fragments that may impede definitive reduction in the operating room. Additionally, early temporary fixation will restore native soft tissue biology and calcaneal morphology allowing for optimal healing conditions prior to definitive fixation.

Given these benefits, external fixators have been studied to treat acute calcaneus fractures definitively, in a brief-(days) or prolonged- (months) staged approach. To date there has only been three case series describing a brief-staged technique with use of an external fixator for treatment of complex calcaneal fractures. Our study will provide the first prospective-randomized controlled trial of this potentially practice changing protocol. The purpose of this study is to compare the efficacy of temporary external fixation vs. splinting for the treatment of acute calcaneal fractures prior to definitive surgical fixation.

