## 6) Study Endpoints and Procedures involved

### I. Design

- Subjects will be recruited from the UC Davis Medical Center. Adults diagnosed with an acute (<1-2 days from injury) calcaneal fracture recommended for operative treatment will be offered enrollment into the study.
- A total of 100 patients will be enrolled in the study. The sample size can be calculated at 35 per treatment groups after considering multiple comparisons and using an 80% power and an  $\alpha = 0.05$ . This would require a minimum of 70 patients for the study; however, factoring in a 30% dropout rate, a minimum of 100 patients will be enrolled into the study with a minimum of 50 patients per group.

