### II. Methods

- Patients will be randomized to one of two treatment groups: temporary external fixation or temporary splinting. Both temporary treatments are those routinely used/available at the UCD health system. Subjects are to wear the temporary treatment method until definitive surgery.
- Safety endpoints occur at conclusion of the definitive fixation of their calcaneal fracture.

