### **III. Outcomes**

#### **Primary outcome**

1. Time to definitive surgery
2. Soft tissue complications (at routine follow ups which are 2, 6, & 12 weeks, and 6, 12, & 24 months after surgery)

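### The 3-year primary analysis date falls at least 12 months before the last 24-month reading of soft tissue complications, and no earlier primary time point or data cut-off is named

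*Combined protocol and SAP*

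**What the plan says.** Section 5 (Study Timelines) gives three dates that have to fit together:

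- Recruitment: "Patient recruitment will take place over two years", with the qualification "however this may be longer depending on the number of patients who require definitive surgery". A shorter period is not mentioned.
- Follow-up: "participation in the study will conclude at two year postoperatively". The clock runs from surgery, not from enrolment.
- Analysis: "The primary analysis will be complete within 3 years of the study start time".

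Section 6.III (Outcomes) lists two primary outcomes. The first is the time to definitive surgery. The second is "Soft tissue complications (at routine follow ups which are 2, 6, & 12 weeks, and 6, 12, & 24 months after surgery". None of the six visits is singled out as primary.

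Section 6.IV (Analysis) plans a comparison between the two groups, an alpha of 0.05, and percentages with 95% confidence intervals for categorical data. It does not say which reading is compared, when the data are cut, or how incomplete follow-up is handled.

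Section 6.II (Methods) adds: "Safety endpoints occur at conclusion of the definitive fixation of their calcaneal fracture". It does not link this sentence to either primary outcome or to the analysis date.

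**The concern.** A primary analysis before the end of follow-up is legitimate when the plan says which earlier reading it uses. Here one primary outcome is scheduled to 24 months, the analysis is due before many patients can reach that visit, and nothing fills the gap. At month 36, anyone operated on after month 12 has no 24-month reading.

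Two analysts following the plan could analyse the 6-month reading, the 12-month reading, only the patients who have reached 24 months, or any complication recorded so far. All would comply, and they could get different answers. Using only the patients who have reached 24 months loses precision. Using any complication so far mixes patients followed for about 11.5 months with patients followed for 24.

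Randomisation should keep follow-up similar in the two arms, so the harm is an undefined primary outcome and lost precision rather than an expected bias between arms. There is also a possible risk that the time point is settled after outcomes are known: section 15 says subjects can see which treatment they receive, and section 9 says complications are tracked as standard care. Nothing in the plan says this will happen.

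**Working it through.** **Inputs from the plan.** Recruitment R = 24 months or more, follow-up of 24 months from surgery, and analysis complete by month 36 (section 5). Readings at 2, 6 and 12 weeks and 6, 12 and 24 months (section 6.III). 100 patients, 50 per arm, 35 per arm evaluable, 80% power, alpha 0.05 and 30% dropout (section 6.I).

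**Assumptions.** The plan gives neither the accrual pattern nor the wait from enrolment to surgery. I take waits of 0, 2 and 4 weeks (0, 0.46 and 0.92 months) and vary the accrual pattern. Section 3 supports a wait above zero: "This delay is necessary for soft tissue swelling to subside prior to surgery".

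**Step 1: the plan's own figures.** The enrolment target reproduces: 70 / (1 − 0.30) = 100. The 3-year date does not. The last 24-month visit is at R + wait + 24 = 24 + 0 + 24 = month 48 at the earliest, and 48 − 36 = 12 months late. With a 2-week wait it is about month 48.5. If recruitment runs 30 or 36 months with no wait, the last visit is at month 54 or 60, which is 18 or 24 months late.

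**Step 2: share with a 24-month reading at month 36.** The share is F(12 − wait), where F is cumulative accrual as a proportion.

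| Accrual | Wait | Share |
|---|---|---|
| Uniform, R = 24 | 0 weeks | 12/24 = 0.500 |
| Uniform, R = 24 | 2 weeks | 11.54/24 = 0.481 |
| Uniform, R = 24 | 4 weeks | 11.08/24 = 0.462 |
| Slow start, (t/R)², R = 24 | 0 weeks | 0.250 |
| Front-loaded, (t/R)^0.5, R = 24 | 0 weeks | 0.707 |
| Linearly falling rate, R = 24 | 0 weeks | 0.750 |
| Uniform, R = 30 | 0 weeks | 12/30 = 0.400 |
| Uniform, R = 36 | 0 weeks | 12/36 = 0.333 |

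**Step 3: consequence if the 24-month reading is the one analysed.** Uniform accrual, R = 24, and dropout assumed unrelated to enrolment date.

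- Patients per arm = 50 × 0.7 × share = 35 × share: 17.5, 16.8 and 16.2 for waits of 0, 2 and 4 weeks.
- Confidence interval width relative to plan = 1/√share: 1.41, 1.44 and 1.47.
- Power, for whatever effect gives 80% at 35 per arm, = Φ((1.960 + 0.842) × √share − 1.960): 0.51, 0.49 and 0.48 at two-sided alpha 0.05. If 0.05 is split over the two primary outcomes, it is 0.48, 0.46 and 0.44.

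**Step 4: what can be complete by month 36.** With R = 24 and a 2-week wait, the last 6-month visit is at 24 + 0.46 + 6, about month 30.5, and the last 12-month visit is at about month 36.5. All patients reach 6 months in every accrual pattern above. For the 12-month reading the share is 0.962 (slow start), 0.981 (uniform), and 0.990 or 0.9996 (front-loaded). The shortest follow-up at month 36 is 36 − 24.46, about 11.5 months.

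**The case against.** The strongest reply is that the date gap is not in itself an error. Section 5 lists the end of participation and the completion of the primary analysis as separate milestones, which fits a primary analysis followed by longer-term follow-up. That is fair as far as it goes, and it shows where the defect lies: the plan never says which earlier reading the primary analysis uses. It does not remove the defect.

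The 12-month gap also depends on recruitment taking its planned two years. If it took 18 months, the last 24-month visit would be at month 18 + 24 = 42 plus the wait, a gap of at least 6 months. This stands as a condition on the figure, but section 5 allows only for a longer period.

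The fall in power applies only if the 24-month visit alone is analysed. The outcome can equally be read as complications recorded across all visits, in which case every patient still in follow-up contributes about 11.5 months or more under on-time recruitment with a 2-week wait. The 80% starting point is itself tied to no outcome or effect in section 6.I. Both points stand. The power figures show the cost of one permitted reading and are not a forecast. Likewise, the half-month shortfall at 12 months is trivial against dates given in round years.

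The section 6.II sentence on safety endpoints does not rescue the date. It does not mention the primary analysis, and every scheduled reading of soft tissue complications comes after surgery, so using it as a cut-off would leave none of them.

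Finally, a time-to-first-complication analysis, censored at a pre-specified cut-off, would use all follow-up and could keep the 3-year date. That is a reasonable alternative, but the plan does not contain it.

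**Conclusion.** The concern holds and should be fixed. Under the planned two-year recruitment, the primary analysis is due at least 12 months before the last 24-month reading of a primary outcome, and the plan names no earlier time point, cut-off or rule for partial follow-up. The 12-month minimum needs no assumption beyond recruitment lasting the planned two years.

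The share of patients with a 24-month reading at month 36 is about half under uniform 24-month accrual, and runs from 25% to 75% across the other 24-month patterns tried. The losses in sample size, interval width and power apply only if that reading is the one analysed. Time to definitive surgery can be complete by month 36 if recruitment is on time, and so can complications through 6 months. The problem is fully correctable because the 24-month data are to be collected in any case.

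**What to change.** Replace the 3-year date with one tied to the last patient's visit at a single named time point for soft tissue complications, fixed before outcome data are examined. There are two ways to do this:

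- **(a) Keep 24 months.** State that the primary analysis of this outcome follows the last 24-month visit, at month 48 or later. This delays its primary report by at least one year.
- **(b) Name one earlier fixed window after surgery**, for example 6 or 12 months. Analyse it once the last patient completes it, and report later complications as secondary. With a 2-week wait and on-time recruitment, a 6-month window ends at about month 30.5 and can meet year 3. A 12-month window ends at about month 36.5 and slightly overruns it. Late complications become secondary, and the sample size basis may need restating, since section 6.I ties it to no outcome.

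If the sponsor prefers to use all follow-up at a calendar date, a time-to-first-complication analysis with a pre-specified cut-off and censoring rule would also settle the point.

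In each case, state when time to definitive surgery is analysed, and reconcile the section 6.II sentence on safety endpoints with the complication readings scheduled after surgery in section 6.III. The cost is a protocol amendment to the timeline and the outcome definition. Visits and data collection stay as they are.

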## 6) Study Endpoints and Procedures involved

### I. Design

- Subjects will be recruited from the UC Davis Medical Center. Adults diagnosed with an acute (<1-2 days from injury) calcaneal fracture recommended for operative treatment will be offered enrollment into the study.
- A total of 100 patients will be enrolled in the study. The sample size can be calculated at 35 per treatment groups after considering multiple comparisons and using an 80% power and an  $\alpha = 0.05$ . This would require a minimum of 70 patients for the study; however, factoring in a 30% dropout rate, a minimum of 100 patients will be enrolled into the study with a minimum of 50 patients per group.

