**2) Objectives**

Aim:

- Determine if external fixation decreases soft tissue complications compared to splinting.
- Determine if external fixation decreases time to definitive surgical stabilization and improves final fixation compared to splinting.
- Determine if external fixation improves functional outcomes as evaluated by validated functional scoring systems.

Hypothesis:

- External fixation improves definitive fixation and functional outcomes of acute calcaneal fractures with decreased complication rates compared to splinting

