#### **Secondary outcomes**

1. Union rate via standard weight bearing plain radiographs ( harris axial/lateral views) at 6 weeks, 12 weeks, 6 months, 1 year, and 2 years after surgery. We will also obtain a 1X CT scan of the injured foot at 1 year after surgery to monitor for arthritic progression.
2. Radiographic parameters(Bohler's angle, clancaneal height/width/length, and angle of Gissan)
3. Other complications
4. Clinical outcomes will be evaluated to monitor patients' activity levels, pain, and functional status. This will be done primarily using the web-based Surgical Outcome System™ (SOS)
  - The SOS is currently a UCD IRB approved study (IRB # 1192222). It is a large international web-based registry that permits collection of baseline characteristics of patients undergoing orthopedic procedures. The data is collected using direct entry into a web-based collection system called the Surgical Outcome System (SOS). By completing these surveys, the investigator surgeon has the opportunity to monitor the subjects progress after treatment, even when they are not scheduled to see the provider. The investigator surgeon will also be able compare the outcomes to the average de-identified global data.
  - In order to utilize the web-based surveys, we would invite patients to dual enroll and consent into SOS. If, the subject forgoes SOS participation, the surveys may be filled out manually and this data will not be part of SOS.
  - Subjects fill out surveys before visits at 7 total time points: preoperatively, & postoperatively at 2, 6, and 12 weeks and 6 months, 1 and 2

**PROTOCOL TITLE:** Staged External Fixation of Acute Calcaneal Fractures

years. The surveys may include the Visual Analogue pain score(VAS), Patient-reported outcomes measurement information system 10 short form (PROMIS 10), or Veterans RAND 12 item Health survey (VR-12), Foot function index questionnaire (FFI-R) or Foot and Ankle Ability measure activities of daily living (FAAM ADL), and FAAM sport

**IV. Analysis:** The data will be analyzed for differences between splinting and external fixator treatment groups. Data will be stratified and analyzed for further differences in outcomes based on other factors (ie: demographics, comorbidities..)

- To assess significance the alpha level will be set at <0.05.
- Continuous data will be reported as means, standard deviation(SD), range, with 95% confidence intervals

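### Two primary outcomes share one stated alpha of 0.05; the success rule, a single complication endpoint and the outcome behind the 80% power are not stated

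*Combined protocol and SAP*

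**What the plan says.** All references are to the combined protocol and SAP.

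- **Section 6, III. Outcomes** lists two primary outcomes: "Time to definitive surgery" and "Soft tissue complications (at routine follow ups which are 2, 6, & 12 weeks, and 6, 12, & 24 months after surgery". No single visit or cumulative definition is chosen for the second.
- **Section 2, Objectives** makes both of these aims: complications in the first, time to stabilization in the second. The hypothesis reads "External fixation improves definitive fixation and functional outcomes of acute calcaneal fractures with decreased complication rates compared to splinting". It covers complications but not time to surgery, and sets no rule for success.
- **Section 6, I. Design** says "The sample size can be calculated at 35 per treatment groups after considering multiple comparisons and using an 80% power" and an alpha of 0.05, and then "factoring in a 30% dropout rate, a minimum of 100 patients will be enrolled into the study". It does not name the outcome, the effect size, the number of comparisons or the adjustment.
- **Section 6, IV. Analysis** gives one decision threshold: "To assess significance the alpha level will be set at <0.05". It adds "Data will be stratified and analyzed for further differences in outcomes based on other factors" and descriptive reporting with 95% confidence intervals. It gives no test for either primary outcome, and no alpha split, order or success rule.

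**The concern.** The design section shows that the sponsor recognised the multiplicity, but the analysis section has nothing to match it. An allowance in the sample size controls error only if the analysis then uses the corresponding threshold. The stated 0.05 can be read as the level for each outcome or as the overall level. On the second reading, the per-test level is missing.

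If one primary outcome is significant and the other is not, the plan cannot say whether the trial succeeded, and the answer could be chosen after the results are known. Six complication visits with no chosen endpoint widen that choice.

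Because the 80% power belongs to no named outcome, a non-significant complication result could also be read as absence of benefit when power for it may have been low.

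**Working it through.** **Inputs from the plan:** 35 per group, 80% power, alpha 0.05, 30% dropout, at least 50 enrolled per group, two primary outcomes. **Assumed, because the plan gives none:** complication rates, the tests, two-sided testing, and the correlation between outcomes.

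**1. The plan's own figures.** The dropout step reproduces: 35/(1 - 0.30) = 50 per group and 70/(1 - 0.30) = 100 in total. The 35 itself cannot be reproduced or refuted, because no effect size, SD, event rate or hazard ratio is given.

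**2. Either outcome suffices, each tested at 0.05.** With independent outcomes, familywise error = 1 - (1 - 0.05)(1 - a), where a is the exact type I error of the complication test, found by enumerating all 2x2 tables. Rates run from 10% to 40% in 1-point steps.

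| Evaluable per arm | Test | Familywise error |
|---|---|---|
| 35 | Fisher | 6.2-7.8% |
| 35 | Chi-square | 9.5-10.5% |
| 50 | Fisher | 6.7-8.0% |
| 50 | Chi-square | 9.7-10.2% |

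For two tests of exact size 0.05, the independent case is 1 - 0.95 x 0.95 = 9.75%. A bivariate normal calculation gives 9.1% at correlation 0.5 and 7.8% at 0.8. Some correlation is plausible, since section 3 ties the wait to swelling: "This delay is necessary for soft tissue swelling to subside prior to surgery". The choice among six visits is not counted in any of these figures.

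**3. Both outcomes required.** No alpha adjustment is needed. With 80% power on each, joint power is 0.80 x 0.80 = 64% if independent, 69% at correlation 0.5 and 73% at 0.8.

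**4. What the sample size can detect.** For time to surgery, if a two-sample t-test is used, the differences detectable with 80% power are:

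| Evaluable per arm | Alpha 0.05 | Alpha 0.025 |
|---|---|---|
| 35 | 0.68 SD | 0.75 SD |
| 50 | 0.57 SD | 0.62 SD |

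If it is analysed as time-to-event and all 70 patients reach surgery, the detectable hazard ratio is exp[(z for alpha/2 + z for power)/sqrt(70 x 0.25)]. That is 1.95 at alpha 0.05 and 2.09 at 0.025.

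For complications, exact power to detect a halving at alpha 0.05 (Fisher to chi-square) is:

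| Assumed splint-arm rate | 35 per arm | 50 per arm |
|---|---|---|
| 20% | 13-22% | 19-30% |
| 30% | 23-32% | 35-44% |
| 40% | 36-45% | 52-60% |

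So 80% power for one primary outcome does not imply 80% for the other. As an illustration of precision, for 30% vs 15% the Wald 95% half-width is 1.96 x sqrt[(0.30 x 0.70 + 0.15 x 0.85)/n]. This is 19 points with 35 per arm and 16 with 50. Around a difference of 15 points, both intervals include zero.

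**5. Effect of Holm.** The smaller p-value is tested at 0.025 and, if it passes, the other at 0.05. When neither outcome truly differs, the step 2 calculation with 0.025 in place of 0.05 gives 3.3-4.0% (Fisher) or 4.4-5.3% (chi-square) across 35 and 50 per arm. The slight excess over 5% arises because the chi-square test itself can exceed its nominal level at these sizes.

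**The case against.** The strongest reply is that the design section says multiple comparisons were considered. A natural reading is that 0.05 is the overall level and the 35 already allows for adjustment. That stands as far as it goes. A reader might infer that the trial's error rate is inflated to about 10%, or that 35 per group is too small. The documents support neither inference. The inflation arises only if each outcome is tested at 0.05 and either suffices, and the plan does not say so. What the reply does not supply is the rule that the analysis will apply.

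A reader might also infer from the hypothesis that time to surgery is not a real objective. The second aim in section 2 names it, so both primaries are stated aims. The aims still do not say whether one or both must succeed.

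The size of the effect depends on assumptions. With Fisher's test, 35 per arm and complication rates of 3-9%, the familywise error is only 5.0-6.0%. The t-test for time to surgery is plausible, given the planned means and SDs, but it is not specified. Time to surgery is also known before postoperative follow-up starts, so 35 evaluable per arm is probably a worst case for that outcome.

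Finally, it is tempting to declare everything beyond the two primaries exploratory. Control across two primaries does not need this, and it would demote function, which is a separate aim and part of the hypothesis, as well as the radiographic outcomes.

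**Conclusion.** The point holds as an unstated rule, not as a demonstrated error rate or a wrong sample size. Two primary outcomes are named and multiplicity is acknowledged, but the analysis gives one threshold with no adjustment, order or either/both rule. No complication endpoint is fixed and the 80% power has no outcome attached.

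Under an either-suffices reading at 0.05 each, the familywise error is about 6-8% (Fisher) or about 10% (chi-square). This assumes complication rates of 10-40% and independent outcomes. It is lower if the outcomes are positively correlated or, with Fisher's test, if complications are rarer; selection among visits could raise it. Under a both-required reading there is no inflation, but joint power is 64-73% if each outcome has 80%. The correction is a cheap improvement, and it keeps its value only if made before outcome data are seen.

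**What to change.** Before outcome data are seen, add to section 6, IV. Analysis:

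> *The primary outcomes are time to definitive surgery and the cumulative proportion of patients with any soft tissue complication by [one named visit], tested by Holm at a two-sided familywise alpha of 0.05. Complication results at other visits are supportive.*

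Leave the secondary outcomes as secondary. A fixed testing order, or a both-must-succeed rule with joint power stated, would also close the gap if the sponsor prefers it.

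In section 6, I. Design, state which outcome the 80% power belongs to and on what assumptions. If these cannot be recovered, replace the statement with the detectable effects for time to surgery and the power for complications under assumed rates, as in step 4 of the working. Report the between-group complication difference with a 95% confidence interval; the plan promises intervals but does not say they will cover the difference. Do not read a non-significant complication result as no benefit.

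**Cost.** Protocol wording only, with no added enrolment. If the 35 was sized at an unadjusted 0.05 for a t-tested outcome, power at Holm's stricter step is about 71% with 35 evaluable per arm and 87% with 50. If it was already sized at 0.025, nothing is lost. The stated power for complications becomes less favourable: for an assumed halving from 30%, 16-23% at alpha 0.025 with 35 per arm, or 25-33% with 50.
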